## Appendix 9 Modified Japanese Dermatological Association (JDA) Severity Index

	Score			
	0	1	2	3
Assessment of skin lesions				
Area of erythema with pustules	0%	> 0%, < 10%	≥ 10%, < 50%	≥ 50%
Area of erythema (total)	0%	> 0%, < 25%	≥ 25%, < 75%	≥ 75%
Area of edema	0%	> 0%, < 10%	≥ 10%, < 50%	≥ 50%
Assessment of systemic manifestations and laboratory findings				
Fever	<37°C (<98.6 F)	≥ 37°C, < 38.5°C ≥98.6 F, <101.3 F	≥ 38.5°C (≥101.3 F)	–
WBC count	<10,000/μL (<10 × 10  /L)	≥10,000/μL, <15,000 μL (≥10 × 10  /L, <15 × 10  /L)	≥15,000/μL (≥15 × 10  /L)	–
CRP	< 0.3 mg/dL (<3 mg/L)	≥ 0.3 mg/dL, < 7 mg/dL (≥3 mg/L, < 70 mg/dL)	≥7 mg/dL (≥ 70 mg/dL)	–
Serum albumin	≥ 3.8 mg/dL (≥ 38 g/L)	< 3.8 g/dL, ≥3 mg/dL (< 38 g/L, ≥ 30 g/L)	< 3 mg/dL (< 30 g/L)	–
Severity index (total score): 1-6=mild; 7-10=moderate; 11-17=severe				

The table is adapted from Imafuku S, Honma M, Okubo Y, Komine M, Ohtsuki M, Morita A, et al. Efficacy and safety of secukinumab in patients with generalized pustular psoriasis: A 52 week analysis from phase 3 open-label multicenter Japanese study. *The Journal of Dermatology*. 2016;43:1011-1017.

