### 5.1 Inclusion Criteria

Subjects are eligible to be included in the study only if all of the following criteria apply:

1. Male and female subjects must be 18 to 75 years of age inclusive, at the time of signing the informed consent.
2. Have clinically confirmed diagnosis of active GPP.
3. Have a Japanese Dermatology Association severity index total score of  $>6$  **and** must be present with active pustules and erythema accounting for at least 10% of BSA **or** have a GPPPGA score of at least moderate severity.
4. Must be candidates for systemic therapy or phototherapy as assessed by the Investigator.
5. Meet the following laboratory screening criteria:
  - a) Hemoglobin  $\geq 90$  g/L ( $\geq 9$  g/dL)
  - b) White blood cell count  $\geq 3.0 \times 10^9$ /L ( $\geq 3.0 \times 10^3$ / $\mu$ L)
  - c) Platelets  $\geq 100 \times 10^9$ /L ( $\geq 100 \times 10^3$ / $\mu$ L)
  - d) Serum creatinine  $< 132.6$   $\mu$ mol/L ( $< 1.5$  mg/dL)
  - e) Alanine aminotransferase (ALT) and aspartate aminotransferase (AST) levels  $\leq 1.5 \times$  upper limit of normal (ULN)
  - f) Total bilirubin  $\leq 1.5 \times$  ULN. Subjects with known Gilbert's disease who have a serum bilirubin  $< 3 \times$  ULN may be enrolled
6. Body mass index (BMI) of 18 to 36 kg/m^2, inclusive, {BMI = weight (kg)/ [height (m)]}, and total body weight  $> 50$  kg (110 lb).
7. Subjects must be otherwise in a good health as judged by the Investigator based on medical history, physical examination, ECG, hematology, and chemistry laboratory parameters, and urinalysis.
8. Contraceptive use by men or women should be consistent with local regulations regarding the methods of contraception for those participating in clinical studies.

Contraception and pregnancy:

  - A male subject must agree to use contraception as detailed in [Appendix 6](#) of this protocol during the treatment period and for at least 220 days (which includes the duration of relevant exposure plus the duration of sperm cycle) after the study treatment and refrain from donating sperm during this period.
  - Female subjects:

A female subject is eligible to participate if she has a negative serum pregnancy test (beta-human chorionic gonadotropin) at Screening and a negative urine pregnancy test at baseline (see [Appendix 6](#)), is not breastfeeding, and at least 1 of the following conditions apply:

i) Not a woman of childbearing potential (WOCBP) as defined in [Appendix 6](#).

OR

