17.2. SECONDARY EFFICACY

17.2.1. SECONDARY EFFICACY VARIABLES & DERIVATIONS

17.2.1.1. Change in mJDA Severity Index Total Skin Lesions Score At All Study Visits

The mJDA severity index is used to determine the primary endpoint, but itself is not a primary efficacy

variable. Individual components of the mJDA severity index are used for secondary efficacy analysis. Table D shows the mJDA questionnaire.

Table D. Modified Japanese Dermatological Association (mJDA) Worksheet

	Score	Score						
	0	1	2	3				
Assessment of skin lesions	Assessment of skin lesions							
Area of erythema with pustules	0%	>0%, <10%	≥10%, <50%	≥50%				
Total area of erythema	0%	>0%, <25%	≥25%, <75%	≥75%				
Area of edema	0%	>0%, <10%	≥10%, <50%	≥50%				
Assessment of systemic manife	stations and lal	ooratory findings						
Fever (°C)	<37.0	≥37.0, <38.5	≥38.5	n/a				
WBC count (/µL)	<10 000	≥10 000, <15 000	≥15 000	n/a				
CRP (mg/dL)	< 0.3	≥0.3, <7.0	≥7.0	n/a				
Serum albumin (g/dL)	≥3.8	<3.8,≥3.0	<3.0	n/a				

The scores (0 to 3 for skin lesions, and 0 to 2 for systemic manifestations and laboratory findings) as well as the actual values of all seven mJDA assessments will be captured in the eCRF.

The total score will be calculated as follows and is the sum of these 7 scores:

Severity Index Total Score = Sum of scores for: Area of erythema with pustules, Total area of erythema, Area of edema, Fever, WBC count, CRP, Serum albumin The severity index total score will be categorized as follows in the listings: 1-6 = Mild, 7-10 =

Moderate, and 11-17 = Severe.

Severity Index Total score at Visit X = Sum of all 7 mJDA scores at Visit X.

Severity Index Total score at Baseline = Sum of all 7 mJDA Baseline scores.

Change at Visit X = Severity Index Total score at Visit X – Severity Index Total score at Baseline

Descriptive statistics (including n, mean, SD, median, minimum, and maximum) will be presented for each measurement time for all study visits. Each subject's change in mJDA Severity Index Total score will be plotted over all study visits.

The change from Baseline in the mJDA severity index total skin lesions score is the sum of erythema, erythema with pustules, and edema scores. The change in score for each visit can range from -9 to 9 and will be calculated as follows:

Total Skin Lesions Score at Visit X = Sum of the scores at Visit X for: Area of erythema with pustules, Total area of erythema, Area of edema.

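### Protocol Appendix 9 contradicts itself on CRP and albumin units, so a site using the wrong label could mis-score the mJDA total behind entry, CGI category and Week 4 non-response

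*Protocol*

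**What the plan says.** Protocol Section 8.1.2 sends scoring of the mJDA index to Appendix 9, which gives each CRP and albumin cut-off as a leading figure and a bracketed equivalent.

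- CRP, score 0: "< 0.3 mg/dL (<3 mg/L". The two forms agree.
- CRP, score 1: the leading limits are 0.3 and 7 mg/dL, but the bracket reads "≥3 mg/L, < 70 mg/dL", with a different unit at each end.
- CRP, score 2: "≥7 mg/dL (≥ 70 mg/dL".
- Albumin, score 0: "≥ 3.8 mg/dL (≥ 38 g/L".
- Albumin, score 1: "< 3.8 g/dL, ≥3 mg/dL (< 38 g/L, ≥ 30 g/L", with g/dL and mg/dL side by side.
- Albumin, score 2: a leading 3 mg/dL beside a bracketed 30 g/L.

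SAP Section 17.2.1.1, Table D, uses one unit per row: CRP in mg/dL with cut-offs 0.3 and 7.0, and "Serum albumin (g/dL" with cut-offs 3.8 and 3.0. The same section says that the item scores "as well as the actual values of all seven mJDA assessments will be captured in the eCRF", and it defines the total as the sum of the seven scores. It does not say that scores are re-derived from the values. SAP Section 5.4 declares no change from the protocol analysis.

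The total is then used in three places. Inclusion criterion 3 begins "Have a Japanese Dermatology Association severity index total score of" more than 6. Protocol Appendix 8 and SAP Table C turn the change in total into the CGI category, and hence the primary response. Protocol Section 4.1 ends participation for subjects who are non-responders at Week 4.

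**The concern.** Two forms of one cut-off that differ by a factor of 10 or 1000 make neighbouring cells overlap. A CRP of 80 mg/L (8 mg/dL) meets score 2 by the leading figure and score 1 by the bracket. The score then depends on which figure the scorer looks at, and that may differ between sites or between visits for one subject. Section 8.1 only recommends the same assessor throughout.

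One point matters here. A change of −1, 0 or +1 falls in different rows of the CGI table. Entry and Week 4 decisions are taken at the site during the study, so re-scoring at analysis cannot undo them. SAP Section 17.1.2 keeps a Week 4 non-responder as a non-responder at Week 16, and SAP Section 17.1.4 plans no sensitivity analysis.

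**Working it through.** **Conversions.** 1 mg/dL = 10 mg/L = 0.01 g/L, and 1 g/dL = 10 g/L.

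- CRP 0.3 mg/dL × 10 = 3 mg/L, as bracketed.
- CRP 7 mg/dL × 10 = 70 mg/L. The bracketed 70 mg/dL × 10 = 700 mg/L, so it is out by a factor of 10.
- Albumin 3.8 mg/dL × 0.01 = 0.038 g/L against a bracketed 38 g/L; 3 mg/dL × 0.01 = 0.03 g/L against 30 g/L. Both are out by a factor of 1000.
- Albumin 3.8 g/dL × 10 = 38 g/L and 3.0 g/dL × 10 = 30 g/L, so Table D's unit makes every pair agree.

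The item structure itself is sound: 3 × 3 + 4 × 2 = 17, the stated maximum total.

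**Item scores.**

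| Value | Intended score | Score by the wrong label | Loss |
|---|---|---|---|
| CRP <70 mg/L | 0 or 1 | same | 0 |
| CRP 70 to <700 mg/L | 2 | 1 (bracket) | 1 |
| CRP ≥700 mg/L | 2 | 2 | 0 |
| Albumin ≥38 g/L | 0 | 0 | 0 |
| Albumin 30 to <38 g/L | 1 | 0 (score 0 cell, leading figure) | 1 |
| Albumin <30 g/L | 2 | 0 (score 0 cell) or 1 (score 1 cell) | 2 or 1 |

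In the leading figures, an albumin of 33 g/L (3300 mg/dL) meets both the score 0 cell and the mixed-unit score 1 cell, so the literal reading has no single answer.

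**Reading the whole table one way.** Bracketed figures only: albumin is right and CRP can lose 1. Leading figures only: CRP is right and albumin can lose up to 2. Only a mixed reading can lose 1 + 2 = 3.

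**Entry threshold (total >6).** Losses of up to 1, 2 or 3 points put true totals of 7, 7–8 or 7–9 at risk of falling to 6 or below. Of the 4³ × 3⁴ = 5,184 possible score profiles, 4,050 have a total above 6. Of these, 171 drop to 6 or below with the CRP error, 639 with the albumin error (item always 0) and 882 with both. These are unweighted counts that show what is possible. They are not probabilities.

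**Change in total, illustrative subject.** CRP goes from 120 to 40 mg/L and albumin from 33 to 39 g/L, with the other items fixed at 4 points.

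| Reading | Baseline | Follow-up | Change | CGI row by points |
|---|---|---|---|---|
| Intended units | 4+2+1 = 7 | 4+1+0 = 5 | −2 | Much improved |
| Bracketed only | 4+1+1 = 6 | 4+1+0 = 5 | −1 | Much improved |
| Leading only | 4+2+0 = 6 | 4+1+0 = 5 | −1 | Much improved |
| Both wrong labels | 4+1+0 = 5 | 4+1+0 = 5 | 0 | Minimally improved or No change, by the component criterion |

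Either single reading leaves the response row intact here but moves the baseline total from 7 to 6.

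**Inconsistent reading over time.** CRP is stable at 80 mg/L, scored 1 at Baseline (bracket) and 2 at Week 4 (leading figure), with nothing else changed. The change is +1, which is Worsened and a non-responder. Conversely, a true rise from 40 to 80 mg/L scores 1 and 1 by the bracket, so a one-point worsening is recorded as 0.

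**The case against.** The strongest reply is that nobody would score this way. Every affected cell also prints a correct form, every numeral is right, and an albumin reading that gives every subject 0 would soon be noticed. SAP Table D is headed as a worksheet and has clean units. The eCRF is not among the documents and may score automatically. Actual values are captured, laboratory tests are central (Protocol Section 8.2.7), and efficacy variables have full source verification (Protocol Appendix 2). Much of this stands: it limits how often the error would occur and makes it detectable. It does not settle which figure a site uses, because Section 8.1.2 points to Appendix 9 and the SAP does not state that scores are recomputed.

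A reader might infer that literal scoring changes the total in one fixed way, with the CRP and albumin losses adding up. The documents do not support that. The cells conflict, so there is no single literal result, and the two errors do not both arise under one consistent way of reading. A reader might also infer from the SI-unit reporting in SAP Section 19.2 that sites would look up the bracketed figures. That section governs how results are presented and does not say which figure is used for scoring.

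The effect on decisions is limited too. Inclusion criterion 3 also admits a GPPPGA of at least moderate severity, on the reading that its final alternative stands alone. A zero-point change is still a response if the pustule-area or component criterion is met. No change and Worsened are both non-response.

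**Conclusion.** The unit labels in Appendix 9 are wrong as written: the bracketed CRP 70 in two cells, and three of the four leading albumin cut-offs. Depending on the label followed, the possible loss is 1 point for CRP of 70 to <700 mg/L, or 1 to 2 points for albumin below 38 g/L. That is enough to cross the entry threshold or change a CGI row. CRP below 70 mg/L is unaffected, and so is any scorer who uses the correct form in each cell.

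The documents do not show that any subject would be mis-scored, or that eligibility or the primary result would change. With about 10 subjects, one reclassified response is 1/10 = 10 percentage points, but that holds for any misclassification and does not measure the likelihood of this one. The conclusion assumes that at least some scoring is done from Appendix 9 and that the entered item scores feed the total. The eCRF could confirm or remove that assumption. This should be fixed because the table sets decision thresholds and the correction is nearly free.

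**What to change.** In Protocol Appendix 9, change unit labels only, keeping both unit forms and all numerals, so that the table agrees with SAP Table D:

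- CRP: <0.3, ≥0.3 to <7, ≥7 mg/dL, equal to <3, ≥3 to <70, ≥70 mg/L.
- Albumin: ≥3.8, <3.8 to ≥3.0, <3.0 g/dL, equal to ≥38, <38 to ≥30, <30 g/L.

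In SAP Section 17.2.1.1, state that at least the CRP and albumin item scores are derived by programme from the captured values and units, that the derived total is used for the CGI category and responder status, and that differences from the eCRF-entered scores are listed.

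The cost is a wording correction and a short derivation. No new data, visits or subjects are needed, because the values are already captured. The SAP step cannot replace the protocol correction, since entry and Week 4 decisions are made at the sites.

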**Appendix 10 Psoriasis Area Severity Index Score (PASI)**

Plaque Characteristic	Lesion Score	Head	Upper Limbs	Trunk	Lower Limbs
Erythema	0=None				
Induration/Thickness	1=Slight				
Scaling	2=Moderate				
	3=Severe				
	4=Very severe				
Add together each of the 3 scores for each body region to give 4 separate sums (A).					
Lesion Score Sum (A)					
Percentage Area	Area Score	Head	Upper Limbs	Trunk	Lower Limbs
Area Score (B) Degree of involvement as a percentage for each body region affected (score each region with score between 0-6)	0=0%				
	1=1% - 9%				
	2=10% - 29%				
	3=30% - 49%				
	4=50% - 69%				
	5=70% - 89%				
	6=90% - 100%				
Multiply Lesion Score Sum (A) by Area Score (B), for each body region, to give 4 individual subtotals (C).					
Subtotals (C)					
Multiply each of the Subtotals (C) by amount of BSA represented by that region, i.e. × 0.1 for head, × 0.2 for upper body, × 0.3 for trunk, and × 0.4 for lower limbs.					
Body Surface Area		× 0.1	× 0.2	× 0.3	× 0.4
Totals (D)					
Add together each of the scores for each body region to give the final PASI Score.					

PASI Score =

## Appendix 11      Generalized Pustular Psoriasis Physician Global Assessment Scale

The GPPPGA scale will be used to assess the impact and severity of GPP. The Investigator will rate the impact and severity of disease at each study visit (excluding those that are phone calls) using the following scale.

Score	Wording	Detailed description
0	Clear	Normal skin or post - inflammatory hyperpigmentation, no visible pustules, no scaling or crusting
1	Almost clear	Faint, diffuse pink or slight red erythema, low density occasional small discrete pustules (noncoalescent), superficial focal scaling or crusting restricted to periphery of lesions
2	Mild	Light red erythema, moderate density grouped discrete small pustules (noncoalescent), predominantly fine scaling or crusting
3	Moderate	Bright red erythema, high density pustules with some coalescence, moderate scaling or crusting covering most or all lesions
4	Severe	Deep fiery red erythema, very high density pustules with pustular lakes, severe scaling or crusting covering most or all lesions

The table is adapted from Bachelez H, Choon SE, Marrakchi S, et al. Inhibition of the IL-36 Pathway for the Treatment of Generalized Pustular Psoriasis. *N Engl J Med* 2019; 380:(10).

## Appendix 12      Dermatology Life Quality Index

**The aim of this questionnaire is to measure how much your skin problem has affected your life OVER THE LAST WEEK. Please tick  one box for each question.**

1. Over the last week, how **itchy, sore, painful** or **stinging** has your skin been?  
 Very much    A lot    A little    Not at all
2. Over the last week, how **embarrassed** or **self-conscious** have you been because of your skin?  
 Very much    A lot    A little    Not at all
3. Over the last week, how much has your skin interfered with you going **shopping** or looking after your **home** or **garden**?  
 Very much    A lot    A little    Not at all    Not relevant
4. Over the last week, how much has your skin influenced the **clothes** you wear?  
 Very much    A lot    A little    Not at all    Not relevant
5. Over the last week, how much has your skin affected any **social** or **leisure** activities?  
 Very much    A lot    A little    Not at all    Not relevant
6. Over the last week, how much has your skin made it difficult to do any sport?  
 Very much    A lot    A little    Not at all    Not relevant
7. Over the last week, has your skin prevented you from **working** or **studying**?  
 Yes    No    not relevant  
  
If "No", over the last week, how much has your skin been a problem at **work** or **studying**?  
 A lot    A little    Not at all
8. Over the last week, how much has your skin created problems with your **partner** or any of your **close friends** or **relatives**?  
 Very much    A lot    A little    Not at all    Not relevant
9. Over the last week, how much has your skin caused **sexual difficulties**?  
 Very much    A lot    A little    Not at all    Not relevant

10. Over the last week, how much of a problem has the **treatment** for your skin been, for example by making your home messy, or by taking up time?

Very much  A lot  A little  Not at all  Not relevant

AY Finlay, GK Kahn. Dermatology Life Quality Index (DLQI): A simple practical measure for routine clinical use. *Clinical and Experimental Dermatology* 1994; 19: 210-216.

## Appendix 13 Summary of Changes

### **Protocol ANB019-002: Amendment 1, 15 January 2018**

#### **Replaces: Original Protocol, 12 December 2017**

Section 1.1 Synopsis, Section 4.1 Overall Design and Table 1 Schedule of Activities (footnote)

- Description of Change: Added text to indicate that a minimum 3 hour observation period is required after the first and second subcutaneous injections and deleted from the following text ‘no such limit for study center observation after SC administration’.
- Purpose of Change: Medicines and Healthcare Products Regulatory Agency (MHRA) request.

Section 5.1 Inclusion Criteria and Appendix 6 Contraceptive Guidance and Collection of Pregnancy Information:

- Description of Change: Text revised to specify that in addition to prohibition on sperm donation for the specified duration, ova donation for assisted reproduction is also prohibited. The duration for males was revised to 220 days (from 6 months).
- Purpose of Change: MHRA request.

### **Protocol ANB019-002: Amendment 2, 27 July 2018**

#### **Replaces: Amendment 1, 15 January 2018**

Section 1.1 Synopsis and Section 4.1 Overall Design:

- Description of Change: Text revised to remove a minimum of 7 days screening period requirement and updated ‘up to 28 days’.
- Purpose of Change: To simplify enrollment of newly diagnosed subjects.
- Description of change: Updated the number of Investigators and number of study centers from 3 to 5.
- Purpose of change: To reflect the updated number of Investigators and study centers (administrative change).

Section 2.2 Background (Clinical studies).

- Description of Change: Added the percentage for mild and moderate TEAEs and details about 1 severe AE.
- Purpose of Change: To reflect the updated Phase I Study results (ANB019-001, SAD part).

Section 2.2 Background and Section 2.3 Benefit/Risk Assessment:

- Description of Change: Text revised to include SAD (PP) safety and MAD (healthy volunteers) safety and PK data from the Phase I study (ANB019-001) in healthy volunteers and PP subjects.
- Purpose of Change: To reflect New safety and PK data from the Phase I study (ANB019-001).

### Section 5.1 Inclusion Criteria:

- Description of Change: Added SI and conventional units for hemoglobin, white blood cell count, platelets, and serum creatinine.
- Purpose of Change: To reflect both SI and conventional units for hemoglobin, white blood cell count, platelets, and serum creatinine.

### Section 5.2 Exclusion Criteria:

- Description of Change: Text revised to clarify the requirement to stop all systemic conventional therapies (eg. cyclosporine, methotrexate, and retinoid) the day the study drug is administered.
- Purpose of Change: To clarify the use of systemic therapies in case of tapering washout at study start.
- Description of Change: Revised to remove definition of regular alcohol consumption and excessive smoking
- Purpose of Change: Text removed as definition is not applicable in United Kingdom.

### Section 5.3 1 Meals and Dietary Restrictions:

- Description of Change: Removed Meals and Dietary Restrictions.
- Purpose of Change: Section removed as study centers are not going to provide meal and subjects are allowed to bring meal for themselves.

### Section 6.2 Preparation /Handling/Storage/Accountability

- Description of Change: Text regarding ANB019 storage reworded slightly and deleted the repetitive text
- Purpose of Change: Sentence combined to avoid repetition.

### Section 6.5.1 Rescue Medicine:

- Description of Change: Section revised to include guidance for using rescue medication in the form of topical corticosteroids (eg. betamethasone valerate ointment and cream, mometasone furoate ointment and cream) and guidance for adding any systemic psoriasis medication that is likely to impact psoriasis signs and symptoms (eg. cyclosporine, methotrexate, retinoid).
- Purpose of Change: To provide clarity on rescue medication usage.
- Description of Change: Added text to indicate ‘introduction of any rescue medication must be communicated and discussed with the Sponsor’.
- Purpose of Change: To ensure that use of rescue medication must be communicated and discussed with the Sponsor.

### Section 8.0 Study Assessments and Procedures.

#### Section 8.1.4 Total Body Surface Area (Study Assessments and Procedures).

- Description of Change: Revised to remove the section 8.1.4 describing assessment of body surface area affected by GPP.

- Purpose of Change: Text removed as BSA involvement is measured as part of modified JDA scale.

#### Section 8.2.5 Chest X-ray and Table 1 Schedule of Assessment (footnote).

- Description of Change: Bidirectional posterior-anterior and lateral view chest X-ray or as indicated by local treatment guidelines or practice is updated to include that it will be performed at Screening if not performed within 6 months prior to screening and other time points specified in the Schedule of Activities.
- Purpose of Change: To provide clarity on the time point of X-ray.
- Description of Change: Added text to indicate that ‘In case of early discontinuation, the subject will be encouraged to return to the study center for the follow-up period visits (Week 16/Day 113 and Week 20/Day 141) and ET/EOS visit (Week 24/Day 169). The follow-up period visits are not actual calendar weeks and have to occur 4/8/12 Weeks post-discontinuation.’
- Purpose of Change: To provide clarity in case of early discontinuation and follow-up period (ET/EOS visit).

